7.1.2 Adverse Event

An AE is defined as any untoward medical occurrence, including an exacerbation of a pre-existing condition, in a subject in a clinical investigation who received a pharmaceutical product. The event does not necessarily have to have a causal relationship with this treatment.

Worsening of pre-existing conditions: A pre-existing condition present at baseline, which remains unchanged during the trial, does not need to be recorded as AE.

Any worsening of any pre-existing baseline condition should be reported as an AE in the eCRF. Examples of worsening of a pre-existing condition that should be recorded as an AE are given below:

- Worsening of condition meets the criteria for an AE or SAE
- Action is taken with the investigational drug (e.g. Dose is reduced or treatment is discontinued)
- Treatment is required (concomitant medication is added or changed)
- The Investigator believes a subject has shown a clear deterioration from baseline symptoms

Expected fluctuations or expected deterioration of the EOC (symptoms of disease progression) should not be recorded as an AE.

Changes in vital signs, physical examination and laboratory test results: will only be recorded as an AE in the eCRF if they are judged clinically relevant by the Investigator.

Overdoses: refer to section 7.4.1.

7.1.3 Serious Adverse Event

A serious adverse event is one that at any dose (including overdose):

- Results in death
- Is life-threatening¹
- Requires inpatient hospitalization or prolongation of existing hospitalization
- Results in persistent or significant disability or incapacity²
- Is a congenital anomaly or birth defect
- Is an important medical event³

¹ “Life-threatening” means that the subject was at immediate risk of death at the time of the serious adverse event; it does not refer to a serious adverse event that hypothetically might have caused death if it were more severe.

² “Persistent or significant disability or incapacity” means that there is a substantial disruption of a person’s ability to carry out normal life functions.

³ Medical and scientific judgment should be exercised in deciding whether expedited reporting is appropriate in situations where none of the outcomes listed above occurred. Important medical events that may not be immediately life-threatening or result in death or hospitalization but may jeopardize the subject or may require intervention to prevent one of the other outcomes listed in the definition above should also usually be considered serious. Examples of such events include allergic bronchospasm requiring intensive treatment in an emergency room or at home, blood dyscrasias or convulsions that do not result in inpatient hospitalization, the development of drug dependency or drug abuse, etc.

7.1.3.1 Disease-related events

An event that is part of the natural course of the disease under study (i.e. disease progression) does not need to be reported as an SAE. Progression of the subject’s EOC will be recorded in the appropriate pages of the eCRF. Death due to progressive disease is to be recorded on Death Report Form of the eCRF and not as an SAE.

However, if the Investigator considers that there was a causal relationship between treatment with investigational product or protocol design/procedures and the disease progression, then this must be reported as an SAE. Any new primary cancer must be reported as an SAE.

7.1.3.2 Planned or administrative hospitalization

Subjects may be hospitalized for administrative or social reasons during the trial (e.g. days on which infusion takes place, long distance from home to site...). These and other hospitalizations planned at the beginning of or before the trial do not need to be reported as an SAE in case they have been reported at screening visit in the source data and have been performed as planned.

7.1.3.3 Unexpected Adverse Event

Azacitidine and pembrolizumab IBs provide an overview of the adverse events reported across each drug’s clinical trials in monotherapy and in combination.

Any Serious Adverse Event assessed as related to azacitidine or pembrolizumab but not reported in the listed adverse events' section of the corresponding IB will be documented as a suspected unexpected serious adverse reaction (SUSAR) and will be submitted according to applicable local regulations.

7.1.4 Events of Clinical Interest (ECI) with Pembrolizumab

Selected non-serious and serious pembrolizumab adverse events are also known as ECI and must be reported within 24 hours to the sponsor according to section 7.3.1 during the collection period specified in section 7.1.1.

Any ECI, or follow up to an ECI, that occurs to any subject must be reported immediately to the sponsor if it causes the subject to be excluded from the trial, or is the result of a protocol-specified intervention, including but not limited to washout or discontinuation of usual therapy, diet, placebo treatment or a procedure.

ECIs for this trial include:

- A pembrolizumab overdose (as defined in section 7.4.1) that is not associated with clinical symptoms or abnormal laboratory results.
- An elevated AST or ALT lab value that is greater than or equal to 3X the upper limit of normal and an elevated total bilirubin lab value that is greater than or equal to 2X the upper limit of normal and, at the same time, an alkaline phosphatase lab value that is less than 2X the upper limit of normal, as determined by way of protocol-specified laboratory testing or unscheduled laboratory testing.*

*Note: These criteria are based upon available regulatory guidance documents. The purpose of the criteria is to specify a threshold of abnormal hepatic tests that may require an additional evaluation for an underlying etiology.

7.2 Performing Adverse Event Assessment

7.2.1 Collection of Adverse Event Information

The following information will be collected in the eCRF: Description of event, start/stop date, worst grade experienced (severity), seriousness, action taken on study treatments and relationship to study treatments.

Intensity of adverse event: The intensity of adverse events will be classified and recorded according to the Common Terminology Criteria for Adverse Events (CTCAE) version 4.03 in the eCRF or according to the grading defined in section 5.7.1 if the adverse event is not specifically listed in NCI CTCAE.

All adverse clinical experiences, whether observed by the Investigator or reported by the subject, must be recorded, with details about the duration and intensity of each episode, the action taken with respect to the test drug, and the subject's outcome. The Investigator must evaluate each adverse experience for its relationship to the test drug and for its seriousness.

The Investigator must appraise all abnormal laboratory results for their clinical significance. If any abnormal laboratory result is considered clinically significant, the Investigator must provide details about the action taken with respect to the study treatments and about the subject's outcome.

7.2.2 Assessment of Causality

The Investigator will determine the relationship of the study treatments to all AEs as defined in Single Reference Documents for CC-486 and pembrolizumab (see sections 5.1 and 5.2).

Medical judgment should be used to determine the relationship, considering all relevant factors, including pattern of reaction, temporal relationship, de-challenge or re-challenge, confounding factors such as concomitant medication, concomitant diseases and relevant history. Assessment of causal relationship must be recorded for each adverse event.

Relationship to study drugs will be reported as either “Yes” or “No”.

- Yes: There is a reasonable causal relationship between the investigational product administered and the AE.
- No: There is no reasonable causal relationship between the investigational product administered and the AE.

7.3 Reporting of Serious Adverse Events, Events of Clinical Interest and Pregnancies

7.3.1 Reporting of SAEs/ECIs/Pregnancies from the sites to TRIO

SAEs and ECIs will be reported via the Serious Adverse Event Reporting Form. Pregnancies will be reported via the Pregnancy Reporting Form (refer to section 7.4.2 for more information on reporting pregnancies). The initial report must be as complete as possible, including an assessment of the causal relationship between the event and the investigational product(s). Information not available at the time of the initial report (e.g. an end date for the adverse event or laboratory values received after the report) must be documented on a follow-up report. A final report to document resolution of the SAE is required.

These forms will be faxed or emailed to TRIO Drug Safety and Pharmacovigilance Department to:

- Email: [contact]
- Fax number: North America: + 1 [contact] / Rest of the World: [name]

Table 9: SAE/ECIs and Pregnancies reporting timelines

Type of Event	Initial Reports		Follow-up Information	
	Time Frame	Documents	Time Frame	Documents
All SAEs/ECIs	Immediate	SAE Reporting Form	Immediate	SAE Reporting Form
Pregnancy	Immediate	Pregnancy Reporting Form	Immediate	Pregnancy Reporting Form

7.3.2 SAE/ECl/Pregnancies Information Provided by TRIO to Celgene and Merck

TRIO will report all SAEs and pregnancies to Celgene and Merck by forwarding the SAE Reporting Form or Pregnancy Reporting Form via email or other secure method within 24 hours of site awareness. Additionally, any ECI will be provided by TRIO to Merck also within 24 hours of site awareness. The SAEs/ECIs/Pregnancies will be a copy of the SAE or Pregnancy Reporting Form.

7.4 Management of Specific Cases

7.4.1 Overdoses

CC-486 overdose is defined as the accidental or intentional use of CC-486 in a daily dose ≥ 2 times the indicated dose.

Pembrolizumab overdose will be defined as any dose of 1,000 mg or greater (≥ 5 times the indicated dose).

In the event of overdose, the subject should be observed closely for signs of toxicity. Appropriate supportive treatment should be provided if clinically indicated. There is no known specific antidote for pembrolizumab and/or CC-486 overdose.

If an adverse event(s) is associated with (“results from”) the overdose of a study drug, the adverse event(s) is reported as SAE, even if no other seriousness criteria are met.

If a dose of CC-486 meeting the protocol definition of overdose is taken without any associated adverse event, the overdose should be reported as a non-serious adverse event, using the terminology “accidental or intentional overdose without adverse effect”.

If a dose of pembrolizumab meeting the protocol definition of overdose is taken without any associated clinical symptoms or abnormal laboratory results, the overdose should be reported as a non-serious ECI, using the terminology “accidental or intentional overdose without adverse effect”.

All reports of overdoses associated with SAEs or that are considered ECI must be reported to the sponsor immediately (i.e. no more than 24 hours after learning of the event; section 7.3)

7.4.2 Pregnancy

Given the patient population in the trial, it is extremely unlikely that WoCBP are enrolled and therefore that pregnancies occur in study subjects.

Pregnancies and suspected pregnancies (including elevated β hCG or positive pregnancy test in a female subject of reproductive potential, regardless of disease state) occurring while the subject is on study treatment up to and including 30 days after the subject’s last dose, are considered immediately reportable events. The study treatment is to be discontinued immediately.

The pregnancy, suspected pregnancy, or positive pregnancy test must be reported to TRIO on a Pregnancy Reporting Form (see section 7.3.1). The female subject should be referred to an obstetrician-gynecologist (preferably one with reproductive toxicity experience) or another appropriate healthcare professional for further evaluation.

The Investigator will follow the subject until completion of the pregnancy outcome and a follow up Pregnancy Reporting Form must be submitted at that point with the outcome of the pregnancy (either normal or abnormal outcome). If the outcome of the pregnancy was abnormal (e.g. spontaneous or therapeutic abortion, stillbirth, neonatal death or congenital anomaly) the Investigator should report the abnormal outcome as an AE. If the abnormal outcome meets any of the serious criteria, it must be reported as an SAE to TRIO Drug Safety and Pharmacovigilance Department immediately, within 24 hours of the Investigator’s knowledge of the event using the SAE Reporting Form.

All neonatal deaths that occur within 28 days of birth should be reported, without regard to causality, as SAEs. In addition, any infant death after 28 days that the Investigator suspects is related to the in utero exposure to the IMP should also be reported to TRIO immediately by facsimile, or other appropriate method, within 24 hours of the Investigator’s knowledge of the event using the SAE Report Form, or approved equivalent form.

The investigator will be responsible to follow-up on all information regarding a reported drug exposure during pregnancy.

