 - International Normalized Ratio (INR) or Prothrombin Time (PT) $\leq 1.5 \times$ ULN unless subject is receiving anticoagulant therapy as long as PT or PTT is within therapeutic range of intended use of anticoagulants
 - Partial Thromboplastin Time (PTT) or Activated Partial Thromboplastin Time (aPTT) ≤ 40 seconds unless subject is receiving anticoagulant therapy as long as PT or PTT is within therapeutic range of intended use of anticoagulants
12. For women of childbearing potential*, negative serum pregnancy test within 7 days of enrollment in Part A or randomization in Part B.
13. Women of childbearing potential* must agree to use acceptable methods of birth control starting with the screening visit and up to 120 days after the last dose of study treatment. Recommendation is for 2 effective contraceptive methods during the study. Adequate forms of contraception are double-barrier methods (condoms with spermicidal jelly or foam and diaphragm with spermicidal jelly or foam), oral depo-provera, or injectable contraceptives, intrauterine devices, and tubal ligation.

14. Willingness and ability to comply with scheduled visits, treatment plan, laboratory tests, and other trial procedures.

** Note: Given the patient population in the trial, it is highly unlikely that women of childbearing potential (WoCBP) are enrolled. WoCBP are any women between menarche and menopause who have not been permanently or surgically sterilized and are capable of procreation. Permanent sterilization includes hysterectomy and/or bilateral oophorectomy and/or bilateral salpingectomy but excludes bilateral tubal ligation/occlusion. Non-sterile women will be considered of WoCBP if they did not have at least 12 months with no menses without an alternative medical cause.*

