20. Known psychiatric or substance abuse disorders that would interfere with cooperation with the requirements of the trial.
21. Prior treatment with any anti-PD-1, or PD-L1 or PD-L2 agent; or with azacitidine (any formulation) or any other hypomethylating agent; or with anti-CD137, or anti-CTLA-4 antibody (including ipilimumab) or any other antibody or drug specifically targeting T-cell co-stimulation or checkpoint pathways.
22. Known or suspected hypersensitivity to azacitidine, pembrolizumab or the excipients of any of the study drugs (including mannitol). Known or suspected hypersensitivity to monoclonal antibodies.

23. Currently participating and receiving study therapy or has participated in a study of an investigational agent and received study therapy or used an investigation device within 4 weeks prior to enrollment in Part A or randomization in Part B.
24. Pregnant or lactating women or is expecting to conceive children or breastfeed within the projected duration of the trial, starting with the screening visit through 120 days after the last dose of trial treatment.

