5.6.1 Contraception

Given the patient population in the trial, it is highly unlikely that WoCBP are enrolled in the TRIO026 study (refer to section 4.1 for the definition of WoCBP).

WoCBP may be included only if they agree to acceptable contraception starting with the screening visit and up to 120 days after the last dose of study treatment.

WoCBP must agree to avoid becoming pregnant by complying with one of the following:

(1) practice abstinence† from heterosexual activity;

OR

(2) use (or have their partner use) acceptable contraception during heterosexual activity.

Acceptable methods of contraception are‡:

- Single method (one of the following is acceptable):
 - intrauterine device (IUD)
 - vasectomy of a subject's male partner
 - contraceptive rod implanted into the skin
- Combination method (requires use of two of the following):
 - diaphragm with spermicide (cannot be used in conjunction with cervical cap/spermicide)
 - cervical cap with spermicide (nulliparous women only)
 - contraceptive sponge (nulliparous women only)
 - male condom or female condom (cannot be used together)
 - hormonal contraceptive: oral contraceptive pill (estrogen/progestin pill or progestin-only pill), contraceptive skin patch, vaginal contraceptive ring, or subcutaneous contraceptive injection

†Abstinence (relative to heterosexual activity) can be used as the sole method of contraception if it is consistently employed as the subject's preferred and usual lifestyle and if considered acceptable by local regulatory agencies and ERCs/IRBs. Periodic abstinence (e.g. calendar, ovulation, symptom-thermal, post-ovulation methods, etc.) and withdrawal are not acceptable methods of contraception.

‡If a contraceptive method listed above is restricted by local regulations/guidelines, then it does not qualify as an acceptable method of contraception for subjects participating at sites in this country/region.

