7. SAFETY MONITORING

7.1 Definitions

7.1.1 Period of Observation

At each visit and any contact during the study and follow-up period, the Investigator or designee will inquire about the occurrence of AEs and will document them in the subject file.

The Investigator or designee will report the AEs in the eCRF and to TRIO Drug Safety and Pharmacovigilance Department when required as per the table below:

Table 8: Reporting period of AEs/SAEs

Study period	AEs (non-serious)		Serious Adverse Events/Pembrolizumab Events of Clinical Interest (ECI)	
	Part A	Part B	Part A	Part B
From PICF to first dose	Not required to report	Only if related to study participation	Only if related to study participation	Only if related to study participation
Study treatment period until End of Treatment visit	All (regardless of relationship)	All (regardless of relationship)	All (regardless of relationship)	All (regardless of relationship)
From End of Treatment visit until End of subject participation ¹	Only if related to study treatment	Only if related to study treatment)	All (regardless of relationship)	Only if related to study treatment

¹ The applicable events as per the table that are ongoing at time of the End of Treatment visit should be followed up to resolution or until the event becomes stable (or returns to baseline) or is unlikely to resolve further in the opinion of the Investigator. Regarding SAEs, in Part A all should be reported/ followed after the End of Treatment visit, regardless of the relationship with the study drugs. In Part B, only study-drug related SAEs should be followed/ reported.

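### The pregnancy reporting window in protocol section 7.4.2 ends 30 days after the last dose, but the protocol's contraception period runs to 120 days, and days 31 to 120 carry no express reporting duty

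*Protocol*

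**What the plan says.** Four places in the protocol set a period after the last dose that bears on pregnancy.

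- **Section 7.4.2 (Pregnancy).** Pregnancies and suspected pregnancies are immediately reportable if they occur while the subject is "on study treatment up to and including 30 days after" her last dose. The investigator then follows the subject to the outcome of the pregnancy, whether normal or abnormal.
- **Section 4.1, inclusion criterion 13.** The commitment asked of any subject who could become pregnant is this: "use acceptable methods of birth control starting with the screening visit and up to 120 days after the last dose of study treatment".
- **Section 4.2, exclusion criterion 24.** Women who are pregnant or lactating, or who expect to conceive or breastfeed, are excluded for a period "starting with the screening visit through 120 days after the last dose of trial treatment".
- **Section 5.6.1 (Contraception).** Such women may enter only if they agree to "acceptable contraception starting with the screening visit and up to 120 days after the last dose of study treatment".

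The synopsis repeats the 120 days in its eligibility criteria. Section 7.3.1 says that "Pregnancies will be reported via the Pregnancy Reporting Form" and refers to 7.4.2 for detail. Its Table 9 sets the timeline for a report but no period of its own. No passage explains why one period is 30 days and the other 120.

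**The concern.** The protocol keeps a full set of provisions for women of childbearing potential: a serum pregnancy test at screening, a contraception commitment, an exclusion for intended conception, and follow-up of any reported pregnancy to its outcome. The last of these stops well before the contraception commitment does. A subject who conceives on day 60 has conceived within the period in which the protocol asked her to avoid it, yet no one is told to report the pregnancy or learn how it ended.

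What is at stake is completeness of safety information after exposure to two agents, one of which section 5.4.2.1 describes as cytotoxic. A pregnancy in that interval with a normal outcome would leave no trace in the safety data. One with an abnormal outcome would be captured only in some circumstances. Nothing in the efficacy analysis depends on this.

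**Working it through.** There is no sample size, event count or power figure in the plan to reproduce on this point. The check compares two calendar windows and then asks whether any other text closes the gap.

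**Inputs**

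| Item | Days after last dose | Source |
|---|---|---|
| Pregnancy reporting window | 30 | Protocol 7.4.2 |
| Contraception | 120 | Protocol 4.1 (criterion 13), 5.6.1 |
| No expectation of conceiving or breastfeeding | 120 | Protocol 4.2 (criterion 24) |
| End of Treatment visit | 30 ± 7, i.e. 23 to 37 | Protocol 6.3.3 |

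**Size of the gap**

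- Uncovered days: 120 − 30 = 90 (days 31 to 120).
- Share of the contraception window after the last dose: 90 / 120 = 0.75.
- If the two windows had the same length, the gap would be 0 days.

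**Does other text close it?**

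1. *Sections 7.3.1 and 7.3.2.* The first gives the form and timing. The second has the sponsor forward pregnancy reports to the two drug suppliers. The sponsor can forward only what sites send, and the sites' stated duty is the one in 7.4.2.
2. *Table 8 (section 7.1.1).* It covers adverse events, serious adverse events (SAEs) and pembrolizumab events of clinical interest. Pregnancy has no row, and an uncomplicated pregnancy is none of these.
3. *SAEs after End of Treatment.* A congenital anomaly is an SAE under section 7.1.3. The footnote to Table 8 says that "in Part A all should be reported/ followed after the End of Treatment visit", while in Part B "only study-drug related SAEs should be followed/ reported". Either route lasts only until the end of the subject's participation.
4. *Neonatal and infant deaths.* The sentences on these in 7.4.2 state no 30-day limit of their own, so such deaths could be reported.
5. *Scheduled contacts in Part A.* Section 6.3.3 makes End of Treatment the last visit for subjects who stop for immune-related progression and have no ongoing SAE or treatment-related event. For them, participation ends at about day 30, so route 3 ends there too.
6. *Scheduled contacts in Part B.* After progression, section 6.3.4.2 provides contact every 6 months, by visit or telephone, for survival status. At the SAP's conversion (section 3.2.4), 6 × 30.4375 = 182.6 days. Assuming the interval starts at or after the last dose, the first such contact falls after day 120. Subjects who stop without progression are seen every 12 weeks, but for tumor assessment and CA-125.
7. *Pregnancy tests.* Tables 6 and 7 schedule none at End of Treatment or in follow-up.

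Routes 3 and 4 capture some abnormal outcomes. None of the seven creates a duty to report a pregnancy arising on days 31 to 120, or to follow one that ends normally.

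**The case against.** The best defense is that the two windows have different purposes and do not contradict each other. The 120 days is a commitment by the subject; the 30 days is a duty on the site, timed to the End of Treatment visit. A site can comply with both. That is true, and it is why this is a gap to reconcile or justify and not a logical contradiction.

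A reader might infer that the protocol defines a 120-day period of risk or exposure and then fails to monitor it. The documents do not support that. They never describe the 120 days in those terms and give no rationale for its length; it could be a cautious margin. Reading it as a risk period is natural, but it is an inference.

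A reader might also infer that three quarters of exposed pregnancies would go unreported. That does not follow either. The 75% is a share of calendar days. Some abnormal outcomes have the partial routes set out in the working, and section 7.1.1 requires enquiry about adverse events at every contact during follow-up.

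Finally, numbers will be tiny. Debulking surgery is an entry requirement (section 4.1, criterion 4). Hysterectomy, bilateral oophorectomy or bilateral salpingectomy takes a woman out of the childbearing category under the note to section 4.1. Sections 4.1, 5.6.1 and 7.4.2 all expect such women to be very rare in the trial. This stands in full. It limits the severity but does not supply the missing requirement, because the protocol chose to legislate for these women.

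**Conclusion.** The point holds in a limited form. A pregnancy arising on days 31 to 120 after the last dose lies within the contraception period the protocol imposes but has no express reporting or outcome follow-up requirement. The gap is 90 of 120 days, and the protocol neither closes nor explains it.

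Severity is the lowest. Few subjects, if any, are concerned, and no endpoint, analysis population, error rate or power figure is affected. The conclusion rests on the protocol text alone. The consent form was not available for review, so it may already ask subjects to tell the site about a later pregnancy. The review takes no view on how long contraception should last.

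**What to change.** Reconcile section 7.4.2 with sections 4.1, 4.2 and 5.6.1 so that the pregnancy reporting window covers the contraception window the protocol already states, or add a sentence saying why the two differ. No dose, treatment or contraception rule needs to change.

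If the windows are aligned, ask subjects in both parts to notify the site of a pregnancy within that window. This matters for Part A subjects who leave the study at End of Treatment, and equally for Part B subjects in six-monthly survival follow-up, since that contact alone would come too late and is not designed to ask about pregnancy. If the consent form does not already include the request, it needs a line there.

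The cost is a short amendment with the usual ethics review (section 9.4) and a small notification duty after treatment ends. For some Part A subjects, that duty would extend beyond their last study visit.
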